9.1. Adverse Events

All the Adverse Events (AE) will be coded using the MedDRA version 21.0 or higher. The severity of an AE will be graded 1 to 5 using the following criteria by the investigator.

- Grade 1 No interference with activity
- Grade 2 Some interference with activity not requiring medical intervention
- Grade 3 Prevents daily activity and requires medical intervention
- Grade 4 Emergency room visit or hospitalization
- Grade 5 Fatal

For any AE that is proven to start or worsen on or after the day of first administration of study drug will be categorized as a treatment-emergent AE (TEAE). An SAE is defined as any event that results in death, is immediately life-threatening, requires inpatient hospital or prolongation of existing hospitalization, results in persistent or significant disability/incapacity, or is a congenital anomaly/birth defect. A Treatment-related TEAE is defined as TEAE which is considered to be related to the study drug and reported as “Possible”, “Probable” or “Definite” on the CRF. Any TEAE with a missing relationship will be classified as a treatment-related TEAE.

For the following AE categories, number and percentage of subjects who experience any TEAE, and the number of event will be summarized by treatment group for each system organ class (SOC) and preferred term (PT), with SOCs and PTs within each SOC presented in a descending order of subject incidence within treatment groups from high dose to low dose and placebo group.

- All TEAEs
- Treatment-related TEAEs
- All SAEs
- Treatment-related SAEs
- Grade 3 or 4 TEAEs
- Grade 3 or 4 treatment-related TEAEs
- TEAEs leading to treatment modification or discontinuation
- TEAEs leading to death

An overview summary of the above AE categories will be provided by treatment group, showing the number and percentage of subjects who experience specific events and the number of events.

Summary table of All TEAEs by maximum toxicity grade will also be provided by treatment group. If subject reports multiple occurrences of a specific AE, the subject will be counted only once on the maximum grade.

Separated listings will be prepared for All TEAEs, SAEs, Grade 3 or 4 TEAEs, TEAEs leading to treatment modification or discontinuation and TEAEs leading to death. The verbatim term, PT and SOC, as well as event dates and other attributes that were collected on CRF will be included in the listing.

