6.4.5 Adverse Events

6.4.5.1 Definitions of Adverse Events

An AE is any adverse change from the subject's baseline conditions, ie, any unfavorable and unintended sign, including an abnormal laboratory findings, symptoms or disease, that occurs during the course of the study, whether or not considered related to the study drug.

A TEAE is defined as any event not present before exposure to study drug or any event already present that worsens in either intensity or frequency from study drug initiation until after the last dose of study drug whether or not considered related to the study drug. The

Investigator is responsible for reporting all TEAEs that are observed or reported during the study, regardless of their relationship to study drug or their clinical significance.

An elective surgery/procedure scheduled to occur during the study will not be considered an AE if the surgery/procedure is being performed for a pre-existing condition and the surgery/procedure has been pre-planned prior to study entry.

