6.4.5.3 Eliciting and Documenting Adverse Events

Adverse events will be assessed and reported from the time the subject takes the first dose of IMP until and including the EOS visit (Visit 7).

All SAEs occurring after signing the ICF must be reported (whether considered associated or not associated to study design or study-mandated procedures).

If the Investigator becomes aware of an SAE that occurs after the EOS visit and is assessed by the Investigator as at least possibly related to the study drug, they need to report the SAE.

At every study visit, subjects will be asked a standard nonleading question to explore a response regarding any medically related changes in their well-being. They will also be asked if they have been hospitalized, had any accidents, used any new medications, or changed concomitant medication regimens (both prescription and over-the-counter medications).

In addition to subject observations, AEs identified from any study data (eg, laboratory values, physical examination findings, ECG changes) or identified from review of other documents that are relevant to subject safety will be documented on the AE page in the eCRF.

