4.6. Imputation of Incomplete Medication Date

For the purpose of inclusion in prior and/or concomitant medication tables, incomplete medication start and stop dates will be imputed as follows:

Missing start dates (where UK, UKN and UNKN indicate unknown or missing day, month and year respectively):

- UK-MMM-YYYY:
 - If the month and year are different from the month and year of the first dose of study drug, assume 01-MMM-YYYY.
 - If the month and year are the same as the first dose of study drug month and year and the end date (after any imputation) is on or after the first dose of study drug, then assume the date of the first dose of study drug.
 - If the month and year are the same as the first dose of study drug month and year and the end date (after any imputation) is prior to the first dose of study drug, then assume the end date for the start date;
- DD-UKN-YYYY/UK-UKN-YYYY:
 - If the year is different from the year of the first dose of study drug, assume 01-JAN-YYYY of the collected year.

- If the year is the same as the first dose of study drug year and the end date (after any imputation) is on or after the first dose of study drug, then assume the date of the first dose of study drug.
- If the year is the same as the first dose of study drug and the end date (after any imputation) is prior to the first dose of study drug, then assume the end date for the start date.

Missing stop dates (where UK, UKN and UNKN indicate unknown or missing day, month and year respectively):

- UK-MMM-YYYY: Assume the last day of the month;
- DD-UKN-YYYY/UK-UKN-YYYY: Assume 31-DEC-YYYY.

If start date is completely missing and end date is not prior to the first dose, then the medication will be classified as concomitant. If the start date is completely missing and the end date is prior to the first dose of study drug, then the medication will be classified as prior. If the end date is completely missing, then the medication will be classified as concomitant. Medications for which both the start and end dates are completely missing will be classified as prior and concomitant.

5. Subject Disposition

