6.1. Demographics

The following characteristics will be summarized:

- Age (years)
- Age category (<65, \geq 65 to <75, \geq 75)
- Sex (Male, Female)
- Race (African American, American Indian or Alaska Native, Asian, Native Hawaiian or other Pacific Islander, White, Other)
- Geographic region (APAC, EMEA, NA)
- Height (cm) and Weight (kg)
- Body mass index (BMI; kg/m²), calculated as BMI (kg/m²) = baseline weight (in kilograms) / height² (in meters).
- Time since RA onset (in years), calculated as date of (informed consent – date of RA diagnosis + 1) / 365.25. If either month or month and day of RA diagnosis date is missing, use the January 1. If day is missing, use the first day of the month. Imputation will not be done for completely missing date.

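### SAP 9.1 requires proof that an AE began or worsened on or after first dose and has no rule for incomplete AE dates, so events of unplaceable onset can be left out of the TEAE tables

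*SAP*

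**What the plan says.** SAP 9.1 categorises "any AE that is proven to start or worsen on or after the day of first administration of study drug" as a TEAE. The same section has a default for one kind of missing AE information: "Any TEAE with a missing relationship will be classified as a treatment-related TEAE". It has none for a missing or partial onset date.

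The SAP handles incomplete dates in two other places. Section 4.6 is limited to medications: "For the purpose of inclusion in prior and/or concomitant medication tables, incomplete medication start and stop dates will be imputed as follows". Section 6.1 covers the diagnosis date: "If either month or month and day of RA diagnosis date is missing, use the January 1".

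Protocol 6.4.5.1 sets no proof condition. It begins "A TEAE is defined as any event not present before exposure to study drug" and adds events already present that get worse. Protocol 6.4.5.3 sets the collection window: "Adverse events will be assessed and reported from the time the subject takes the first dose of IMP until and including the EOS visit". SAEs are collected from the signing of consent. SAP 14 declares no changes to the planned analysis.

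**The concern.** The word *proven* puts the burden on the wrong side for a safety analysis. If the onset of an event cannot be dated relative to Day 1, the event fails the test and by default is not a TEAE. Nearly all AE incidence tables in SAP 9.1 start from that flag: all TEAEs, related TEAEs, Grade 3 or 4 TEAEs, those leading to treatment modification, discontinuation or death, and the table by maximum grade. So does the table of AEs of special interest in SAP 9.2. AE incidence is part of a secondary endpoint (Protocol 7.2, SAP 3.2.2). A rule whose failures all run towards fewer events should not be the default there.

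**Working it through.** The plan states no figure on this point, so the check is mainly of the text.

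**1. Which onset dates fail the test.** SAP 9.1 compares onset with the day of first dose (Day 1).

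| Known part of onset date | Onset on or after Day 1 shown? | Literal result |
|---|---|---|
| Full date | Settled by comparison | Classified as intended |
| Month and year, later than those of Day 1 | Yes | TEAE |
| Month and year, same as Day 1 | No, unless Day 1 is the first of the month | Not a TEAE |
| Year only, later than that of Day 1 | Yes | TEAE |
| Year only, same as Day 1 | No, unless Day 1 is 1 January | Not a TEAE |
| Nothing | No | Not a TEAE |

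A stop date before Day 1 shows that the event is pre-dose. A later stop date does not prove post-dose onset, so it does not rescue an event under this wording.

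**2. How much of each pattern is ambiguous (illustration).** Inputs: 84 days of dosing plus 28 days of follow-up = 112 days (Protocol 3.1). Assumptions not in the documents: true onset uniform over those 112 days, and Day 1 uniform over a 365-day year.

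- *Day missing.* For Day 1 in a month of L days, the days left in that month, counting Day 1, average (L + 1)/2. Summed over all 365 possible start days: 7 × 496 + 4 × 465 + 406 = 5,738. Dividing by 365 × 112 = 40,880 gives 14.0% of post-dose onsets in the same month as first dose. When Day 1 is the first of the month the month alone is proof, which removes 365: 5,373/40,880 = 13.1%. The range by Day 1 runs from 0 to 30/112 = 26.8%.
- *Day and month missing.* 254 start days leave at least 112 days in the year, and the other 111 leave 1 to 111 days: 254 × 112 + 111 × 112/2 = 34,664. Removing the 112 for 1 January gives 34,552/40,880 = 84.5%.
- *Date fully missing.* 100%.

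These are shares of events that already have an incomplete date. How many such events there will be is not in the documents.

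**3. Comparison with the SAP's other defaults.** A TEAE with missing causality counts as related. For a medication, a start date known only to the month or year of first dose is set to the day of first dose, unless the end date is earlier. For a fully missing start: "If start date is completely missing and end date is not prior to the first dose, then the medication will be classified as concomitant". With both dates missing, the medication counts as prior and as concomitant. The same logic applied to AEs would keep the ambiguous events in. The parallel is imperfect, because a medication begun before Day 1 is also concomitant if it continues, so its start date matters less. The direction is still the same.

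**4. Size per subject.** 1/37 = 0.027, or 2.7 percentage points of incidence in an arm of 37. This applies only if the subject has no other event in that table row.

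**The case against.** The best defence is the collection window. If non-serious AEs are recorded only from first dose, each such record is post-dose and the test can be met without a full date. A programmer might well proceed that way. But the SAP does not say that a recorded AE is presumed post-dose, and pre-dose records are possible. SAEs are collected from consent, the schedule of events (Protocol Table 6-1) appears to mark AE monitoring at screening, and Protocol 6.4.5.4 has a screening condition recorded as an AE if it deteriorates at any time during the study. The flag therefore has real work to do and needs a stated rule for incomplete dates. The defence does show that exclusion follows from a literal reading and is not spelled out.

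Four stronger readings are tempting, and the documents do not support them:

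- *All AEs with partial dates are lost.* A later month or year still proves post-dose onset. On the illustration above, about 87% of post-dose onsets with only the day missing remain provable.
- *The events vanish from every AE output.* SAP 9.1 names no listing of all AEs, but Protocol 7.7.5 promises that all safety data will be listed. SAP 9.1 has SAE categories and an SAE listing that are not named as TEAE-only (although the lead-in to the tables speaks of TEAEs), and the SAP 9.2 listing is not restricted to TEAEs.
- *The comparison with placebo is biased.* The rule applies to every arm alike. It lowers absolute counts, and nothing in the documents shows that it does so unequally.
- *The lack of a safety monitoring committee makes it worse.* These tables belong to the single final analysis and would not guide monitoring during the trial.

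It is also fair to say that time of onset is a required AE field (Protocol 6.4.5.4) and that data cleaning is planned (Protocol 8.1), so few records may be affected.

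**Conclusion.** The point stands in a limited form. SAP 9.1 states a positive-proof rule, and no rule for AE dates softens it. Taken literally, AEs with a fully missing onset, or an onset known only to the month or year of first dose, drop out of the TEAE-based incidence tables, including that for events of special interest. This is stricter than the protocol's definition, although SAP 14 reports no changes, and it runs against the inclusive defaults that the SAP uses elsewhere.

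The effect can only lower TEAE counts. Its total size cannot be estimated, since the documents give neither the number of AEs nor the share with incomplete dates. Per subject it is at most about 2.7 percentage points in an arm of 37. The conclusion rests on the literal reading of *proven* and needs none of the calendar assumptions used in the illustration.

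**What to change.** In SAP 9.1, replace the *proven* condition with the protocol's: the event was absent before exposure, or was present and worsened. Then add: *An AE with a missing or partial onset date is treatment-emergent unless the known part of its onset date, or its stop date, shows that it began before first dose and it did not worsen afterwards.*

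Take over only this entry condition without further thought. The protocol's definition also refers to the last dose as an end point, while SAP 9.1 sets no upper limit. That difference should be settled deliberately and not altered as a side effect.

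The cost is one reworded sentence and one new one before database lock. The downside is that an occasional pre-dose event of unknown date is counted as a TEAE, so TEAE rates may be slightly higher. The SAP already accepts that direction of error for missing causality.

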6.4.5.2 Serious Adverse Events

An SAE is defined as any event that results in death, is immediately life-threatening, requires inpatient hospitalization or prolongation of existing hospitalization, results in persistent or significant disability/incapacity, or is a congenital anomaly/birth defect.

Important medical events that may not result in death, be life-threatening, or require hospitalization may be considered SAEs when, based upon appropriate medical judgment, they may jeopardize the subject or require medical or surgical intervention to prevent one of the outcomes listed in this definition. Examples of such medical events include an allergic bronchospasm requiring intensive treatment in an emergency room or at home, blood dyscrasias, convulsions that do not result in inpatient hospitalization, or the development of drug dependency or drug abuse.

Note: The AE terms neutropenia and hypertension should be used only when reporting events that meet the following criteria:

- The term neutropenia is reserved for reporting an absolute neutrophil count (ANC) $<1500/\text{mm}^3$ or $<1.5 \times 10^9/\text{L}$ and may or may not be associated with fever or concurrent infection.
- The term hypertension is reserved for reporting an increase in systolic blood pressure $>160 \text{ mm Hg}$, or diastolic blood pressure $>100 \text{ mm Hg}$, or any clinically significant increase in blood pressure that requires modification of the subject's antihypertensive regimen.

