6.4.5.4 Reporting Adverse Events

All AEs reported or observed during the study will be recorded on the AE page in the eCRF. Information to be collected includes drug treatment, dose, event term, time of onset, Investigator-specified assessment of severity and relationship to study drug, time of resolution of the event, seriousness, any required treatment or evaluations, and outcome.

Adverse events resulting from concurrent illnesses, reactions to concurrent illnesses, reactions to concurrent medications, or progression of disease states must also be reported. Any medical condition that is present at the time that the subject is screened but does not deteriorate should not be reported as an AE. However, if it deteriorates at any time during the study, it should be recorded as an AE.

All AEs will be followed to adequate resolution. The Medical Dictionary for Regulatory Activities (MedDRA) will be used to code all AEs.

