6.8 Pregnancy

Subjects must be counseled during the informed consent process to inform the investigator of any pregnancy that occurs during study participation and for 6 months after the last dose of study drug. In the event of an unexpected pregnancy during study participation or for 6 months after the last dose of study drug, it must be reported via fax or email to PPD within 24 hours of the study site knowledge of the pregnancy via manual Initial Pregnancy Report Form.

For a female subject, the study drug must be discontinued immediately and the subject should inform the Investigator as soon as possible (see Section 4.2). Although study drug will be discontinued, the subject may choose to remain in study and will continue to be monitored for safety while following their regular visit schedule. If the partner of a male subject becomes pregnant, the male subject is not required to discontinue study drug and may remain on the study. The male subject is responsible for informing his partner(s) of the risk of becoming pregnant and for reporting any pregnancy to the Investigator.

The pregnancy must be followed up to determine the outcome (including spontaneous miscarriage, elective termination, normal birth, or congenital abnormality) and the status of mother and child, even if the subject was discontinued from the study, and should be reported to PPD via fax or email on the manual follow-up pregnancy form.

Pregnancy complications and elective terminations for medical reasons must be reported as AEs or SAEs. Spontaneous miscarriages must be reported as SAEs.

Any SAE occurring in association with a pregnancy that is brought to the Investigator's attention after the subject has completed the study and that is considered by the Investigator as possibly related to the study drug must be promptly reported to the sponsor.

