3.2.2. Secondary Endpoints

The secondary efficacy endpoints will be evaluated at Week 2, 4, 8 and 12 unless otherwise stated.

- Percentage of subjects who would achieve American College of Rheumatology (ACR) response (ACR20, ACR50 and ACR70) over time
- Change from baseline in DAS28-hsCRP score (based on 3 individual components including TJC, SJC and hsCRP)

- Change from baseline in the tender/painful and swollen joint count (28)
- Change from baseline in the physician global assessment of disease activity by visual analog scale (VAS)
- Change from baseline in the subject global assessment of disease activity by VAS
- Change from baseline in the subject assessment of arthritis pain by VAS
- Change from baseline in the health assessment questionnaire - disability index (HAQ-DI)
- Change from baseline in median hsCRP values at each schedule visit
- Safety and tolerability of SKI-O-703 compared to placebo including laboratory tests, infections, ECGs, vital signs, incidence of AEs, withdrawals due to AEs and serious adverse events (SAEs).
- PK parameters of SKI-O-592 and its metabolites (M2 and M4) from a subset of subjects per cohort on Day 1 and at Week 12, including: C_{max} , T_{max} , AUC_{0-tau} , $t_{1/2,eff}$, R_{met} , and R_{AUC} , as applicable
- PD parameters for the change from baseline in the percentage of activated gp53/CD63+ basophils in peripheral blood on Day 1 and at Week 12, including: E_{max} , TE_{max} , $AUEC_{0-tau}$, as applicable

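### SAP 9.1 defines an SAE more narrowly than the protocol and has no adverse event summary for stopping study drug alone

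*SAP*

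**What the plan says.** **Serious adverse events.** SAP 9.1 gives its own definition: "An SAE is defined as any event that results in death, is immediately life-threatening, requires inpatient hospital or prolongation of existing hospitalization". The sentence ends with lasting disability and birth defect, which makes five outcomes. It nearly repeats the first paragraph of Protocol 6.4.5.2: "An SAE is defined as any event that results in death, is immediately life-threatening, requires inpatient hospitalization or prolongation of existing hospitalization". The protocol then has a second paragraph that the SAP does not carry: "Important medical events that may not result in death, be life-threatening, or require hospitalization may be considered SAEs when, based upon appropriate medical judgment". Its examples include blood dyscrasias, and convulsions that do not lead to admission. Protocol 6.8 adds: "Spontaneous miscarriages must be reported as SAEs". Section 14 of the SAP declares no changes to the planned analysis.

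**Withdrawals due to adverse events.** The safety item among the secondary endpoints in SAP 3.2.2 (and likewise Protocol 7.2) names "incidence of AEs, withdrawals due to AEs and serious adverse events (SAEs". In SAP 9.1 the only related category is "TEAEs leading to treatment modification or discontinuation". It is used for the table by system organ class and preferred term, for the overview and for a listing. SAP 5.1 separately counts primary reasons for discontinuing treatment, by arm and overall, and repeats this for the study.

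**The concern.** Both SAEs and withdrawals due to AEs are named secondary safety items, and in neither case does SAP 9.1 pin the item down.

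The SAE sentence is a definition by criteria, and it is shorter than the protocol's. A programmer or quality checker who follows it exactly would have grounds to leave out an event that the investigator had validly reported as serious by one of the missing routes.

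The pooled category mixes a temporary pause or a dose reduction with a permanent stop. Protocol Table 3-1 provides for interruption or reduction in response to liver enzyme, neutrophil, blood pressure, gastrointestinal and QTcF findings, and for several of these it reserves the permanent stop for a second occurrence. The pooled row can therefore hold many subjects who never came off drug.

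What is at stake is the comparison of tolerability across three doses. Protocol 3.1.2 says the results will guide further clinical evaluation, and Protocol 1.3 says 400 mg BID has not been studied before in humans. No safety monitoring committee, external data monitoring committee or interim analysis is planned, so the planned comparison by arm rests on the final tables.

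**Working it through.** The documents state no expected SAE or AE-withdrawal rate, so there is no plan figure to reproduce. The check is mainly a comparison of texts.

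**Step 1. Routes to an SAE.**

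| Route | Protocol | SAP 9.1 |
|---|---|---|
| Death | 6.4.5.2 | yes |
| Immediate threat to life | 6.4.5.2 | yes |
| Admission or longer stay | 6.4.5.2 | yes |
| Lasting or significant disability | 6.4.5.2 | yes |
| Birth defect | 6.4.5.2 | yes |
| Important medical event, on medical judgment | 6.4.5.2, second paragraph | absent |
| Spontaneous miscarriage | 6.8 | absent |

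**Step 2. What drives the SAE tables.** Protocol 6.4.5.4 has the AE page collect "time of resolution of the event, seriousness, any required treatment or evaluations, and outcome", and Protocol 6.4.5.5 has SAEs entered on that page against the criteria of 6.4.5.2. The database should therefore hold a seriousness entry that covers the important-medical-event route, and miscarriages should arrive through the same reporting. SAP 9.1 does not say that its SAE tables use this entry. In the same paragraph it ties treatment-relatedness to what is reported on the CRF; the SAE sentence has no such tie. Two readings are thus open: the eCRF entry governs and nothing is lost, or the SAP list governs and the last two rows of the table drop out.

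**Step 3. Where a stop of study drug because of an AE can be seen.**

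- SAP 5.1: counts by primary reason and arm, without system organ class or preferred term. The CRF reason list is not shown; that AE is one of the reasons is inferred from Protocol 4.2.1. That section lists a serious or intolerable AE separately from significant laboratory changes and from intercurrent conditions. If the CRF follows it, a stop driven by a laboratory value could be coded outside the AE reason.
- SAP 9.1 table and overview: pooled with modification.
- SAP 9.1 listing: also pooled, but with event terms and other CRF attributes, so stops could be picked out by hand if the type of action is recorded.

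None of these is a summary, by event and dose, of AEs that led to stopping.

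**Step 4. Scale, for orientation only.** At the planned 37 per arm, one subject is 1/37 = 2.7 percentage points. The rates below are assumptions, not figures from the documents.

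- If a share r of subjects has an SAE by the important-medical-event route alone, the chance of at least one among 148 is 1 − (1 − r)^148. This gives 52% for r = 0.5%, 77% for r = 1% and 95% for r = 2%.
- If 5% of an arm stops drug for an AE, that is 37 × 0.05 = 1.85 subjects. If a further 3% to 20% have only a modification, the pooled row expects 37 × 0.08 = 2.96 to 37 × 0.25 = 9.25 subjects.

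The first range says such an event could plausibly occur, not that it would be lost. The second says the pooled row is no guide to the number who stopped.

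**The case against.** The strongest reply is that nothing will go wrong in practice. Seriousness is the investigator's entry on the eCRF, made under the protocol's full criteria, and nothing in the SAP plans to override it. A reader might infer from SAP 9.1 that the SAE tables will undercount. The documents do not support that: an undercount needs the SAP list to displace the eCRF entry. What stands against the reply is that the SAP leaves the choice open and that its text, followed exactly, conflicts with the protocol.

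On withdrawals, three stronger readings are tempting, and none holds.

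- That withdrawals due to AEs appear only in pooled form. This is true within SAP 9.1 but not of the SAP as a whole, because SAP 5.1 tabulates reasons for stopping treatment and for leaving the study.
- That the SAP breaks a protocol rule. The protocol names the item but gives no derivation for it.
- That the pooled row miscounts. It counts its own stated category correctly; it simply does not isolate the named item.

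It is also fair to say that a cytopenia managed without admission would remain visible. It would appear among all TEAEs, in the neutropenia summary of SAP 9.2 if it affected neutrophils, and in the laboratory grade shifts of SAP 9.3. It would not appear there as serious. With about 37 subjects per arm, the listing can be read by hand. That softens the gap, but a hand count is not a pre-specified summary.

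**Conclusion.** The point holds as two gaps in SAP 9.1.

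1. The SAE definition is narrower than the protocol's by two routes and is not tied to the eCRF seriousness entry. Read literally it gives a wrong count for any SAE reported only by those routes; read with the eCRF entry as the source it does no harm.
2. No AE summary isolates, by event and dose, the events that led to stopping study drug, although the endpoint list names withdrawals due to AEs. SAP 5.1 gives the number who stopped by reason, assuming its CRF categories include AEs, but not the events responsible.

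No size of effect can be derived from the documents, and a demonstrated miscount should not be read into this. No efficacy estimate or test is affected. The correction is still worth making before database lock, because it removes an ambiguity in one named safety item and gives the other a summary of its own at little cost.

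**What to change.** In SAP 9.1:

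- **SAE source.** Replace the five-outcome sentence with a statement that an SAE is any event recorded as serious on the eCRF under Protocol 6.4.5.2 and 6.8, expressly including important medical events and spontaneous miscarriages.
- **Split the pooled category.** Provide separate summaries by system organ class and preferred term, with matching overview rows, for TEAEs leading to (i) dose interruption or reduction, (ii) permanent discontinuation of study drug and (iii), where recorded, withdrawal from the study. State that (ii) and (iii) report the withdrawals item in SAP 3.2.2. Keeping them apart matters because Protocol 4.2.2 lets subjects stop drug and stay in the study.

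The cost is some SAP wording and a few extra tables, with no new data collection, assuming the CRF records the type of action taken with study drug. The field list in Protocol 6.4.5.4 does not name that item, although the pooled category presupposes something like it, so this should be checked against the CRF first.
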